8.3. Clinical Laboratory

Laboratory evaluations including the analyses of chemistry laboratory tests, hematology laboratory tests, urinalysis, and liver function tests will be based on GSK Core Data Standards.

For women who became pregnant on study, a data listing for selected parameters including the following will be provided. Additional parameters of interest may also be listed if applicable.

Clinical Chemistry: Creatinine, GFR, Glucose, HCG

Hematology: HbA1C, Hemoglobin, Hematocrit, Mean Corpuscular Volume, Platelets, Erythrocytes, Lymphocytes, Neutrophils, Basophils, Monocytes, Eosinophils

Immunology: CD4+ cell count, CD8+ cell count, CD4/CD8 cell count ratio, CD4/Lymphocytes, CD8/Lymphocytes

Urinalysis: Albumin/Creatinine, Glucose, Ketones, Occult Blood, Protein, Protein/Creatinine, Erythrocytes

8.4. Biomarker Analyses

Biomarker analysis (renal, bone, inflammation) will not be performed at the Month 6 interim analysis, and will only be performed when all expected data through Month 12 (OLI and BIK)/Month 11 (D2I) has been received from the laboratory. Statistical estimates for each planned visit will be provided in the Month 12 primary analysis using the MMRM model as describe in the below sections unless otherwise noted. The details of the planned displays are in [Appendix 15](#): List of Data Displays.

8.4.1. Bone Biomarkers

Statistical Analyses
Endpoints

 • Change from Maintenance Baseline (Day 1) in the following bone markers at Month 6 (OLI and BIK)/Month 5 (D2I) and at Month 12 (OLI and BIK)/Month 11 (D2I): 
 ◦ Bone-specific alkaline phosphatase ◦ Procollagen type 1 N-propeptide ◦ Type 1 collagen cross-linked C-telopeptide ◦ Osteocalcin ◦ 25 hydroxy-Vitamin D
Covariates

 • Baseline Value (continuous, log-transformed) • Gender at Birth (male, female) • Baseline BMI(<30 kg/m², >=30 kg/m²) • Age (Continuous) • Race (White, Black/African American, Other) • Smoking Status (Never, Former, Current) • Vitamin D use (Yes vs no)

Data Handling

 OC (Observed Case) dataset will be used.
Model Specification

 Analysis values will be log-transformed (including the baseline value). The change in the log-transformed data from Maintenance baseline (i.e. $\log(\text{value}/\text{baseline value})$ or $\log(\text{value}) - \log(\text{baseline value})$) for each bone marker will be analysed for the comparison between the two treatment arms. MMRM (Mix Model Repeated Measures) model with the observed margins (OM) option within PROC MIXED in SAS will be used including treatment group plus the above covariates, with visit as the repeated factor. The Kenward and Roger method for approximating the denominator degrees of freedom and correcting for bias in the estimated variance-covariance of the fixed effects will be used. No assumptions about the correlations between a subject's values will be made (the correlation matrix for within-subject errors will be unstructured). This will be estimated by treatment group by specifying "type=UN" and "group=treatment" options in the SAS MMRM models. In the event that this model fails to converge, alternative correlation structures may be considered such as CSH or CS. Akaike's Information Criteria (AIC) will be used to assist with the selection of covariance structure if needed. The repeated measures analysis will assume that the treatment difference can vary between visits (i.e. a treatment*visit interaction will be included in the model). Estimates and 95% confidence intervals will be produced for each visit.
Model Checking & Diagnostics

 Model assumptions will be applied, but appropriate adjustments maybe made based on the data. Distributional assumptions underlying the model used for analysis may be examined by obtaining a normal probability plot of the residuals and a plot of the residuals versus the fitted values (i.e. checking the normality assumption and constant variance assumption of the model respectively) to gain confidence that the model assumptions are reasonable. If there are any departures from the distributional assumptions, alternative models will be explored using appropriately transformed data.
Model Results Presentation

 For each treatment: Adjusted geometric means (for ratio to Maintenance BL) and 95% CI. Exponential transformation on the estimates from the MMRM model (based on the log-transformed data) will reflect the mean ratio of values post-baseline vs. Maintenance BL for each treatment arm. This ratio can then be translated into percent change from maintenance baseline (Day 1) (e.g. the ratio $bb_{M12}/bb_{bl} = 1.3$ can be translated into 30% increase from baseline). For treatment comparison: Adjusted geometric mean ratio between the two treatment groups (Q2M/BIK), 95% CI and p-value. This ratio can then be translated into percent comparisons in the ratio (value/baseline value) between Q2M vs. BIK (e.g. $Q2M/BIK = 1.2$ can be translated into 20% higher in the Q2M change from baseline ratio compared with BIK).

 Interactions between treatment and each of the covariates will not be assessed but may be explored post hoc.
Sensitivity Analyses

 Not applicable
Subgroup Analyses

 Not applicable

8.4.2. Renal Biomarkers

Statistical Analyses
Endpoints

 Change from Maintenance Baseline (Day 1) in the following renal markers at Month 6 (OLI and BIK)/Month 5 (D2I) and at Month 12 (OLI and BIK)/Month 11 (D2I): 
 Cystatin C Retinol Binding Protein (RBP) Beta-2-Microglobulin (B2M)
Covariates

 Baseline Value (continuous) Gender at Birth (male, female) Baseline BMI(<30 kg/m², ≥30 kg/m²) Age (continuous) Race (White, Black/African American, Other) Hypertension (Yes vs no) Diabetes (Yes vs no) 
Note: Hypertension is defined as having a medical history of hypertension or use of medication treating hypertension (current and past). Diabetes is defined as having a medical history of Diabetes or use of medication treating Diabetes (current and past) or fasting glucose at ≥ 126 mg/dL with HbA1c > 6.5% at Day 1.

Data Handling

 OC (Observed Case) dataset will be used.
Model Specification

 Same as in Section 8.4.1
Model Checking & Diagnostics

 Same as in Section 8.4.1
Model Results Presentation

 Same as in Section 8.4.1
Sensitivity Analyses

 Not applicable
Subgroup Analyses

 Not applicable

CCI

8.5. Other Safety Analyses

The analyses of non-laboratory safety test results including ECGs and vital signs will be based on GSK Core Data Standards, unless otherwise specified. The details of the planned displays are presented in [Appendix 15: List of Data Displays](#).

8.5.1. ECG

ECG Values of Potential Clinical Interest are defined as a QTc of > 500 msec or increase from baseline in QTc ≥ 60 msec.

8.5.2. Metabolic Syndrome

Diagnosis of Metabolic Syndrome is defined as follows per joint interim statement of the International Diabetes Federation Task Force on Epidemiology and Prevention; National Heart, Lung, and Blood Institute; American Heart Association; World Heart Federation; International Atherosclerosis Society; and International Association for the Study of Obesity. Three abnormal findings out of the five risk factors would qualify a person for the metabolic syndrome (waist circumference, triglycerides, HDL, BP and fasting glucose) at each planned time point. See Section 16.6.4 for cutoff details. Percent of subjects diagnosed with metabolic syndrome will be produced. Patient profile as well as listing of clinical diagnosis factors over time may also be provided for those who are diagnosed with metabolic syndrome.

Statistical Analyses
Endpoints

 Proportion of subjects with metabolic syndrome at Month 6 (OLI and BIK)/Month 5 (D2I) and at Month 12 (OLI and BIK)/Month 11 (D2I)
Covariates

 Baseline CD4+ cell count (continuous) Gender at Birth (male, female) Baseline BMI (<30 kg/m², ≥30 kg/m²) Age (35-<50, ≥50, <35 years) Race (White, Black/African American, Other) Smoking Status (Never, Current, Former) Hypertension (Yes vs no) Baseline Triglyceride (High vs. Normal) Baseline HDL (Low, High vs Normal) Baseline HOMA-IR (2 to <3, 3 to <4, ≥4 vs <2) 
Note: Hypertension is defined as having a medical history of hypertension or use of medication treating hypertension (current and past)

Data Handling

 OC (Observed Case) dataset will be used.
Model Specification

 A logistic regression model will be performed on the proportion of subjects with metabolic syndrome at Month 6 (OLI and BIK)/5 (D2I) and at Month 12 (OLI and BIK)/11 (D2I) adjusting for the covariates as above.
Model Checking & Diagnostics

 Upon delivery of data, an assessment regarding the amount of missing data will be made. If the amount of missing outcome data considered as a result of other impacts such as COVID-19 is substantial, the logistic regression analysis may not be performed. If the percent of subjects are below 5% of the total number of subjects (observed data), or if complete or quasi-complete separation is observed in the data, then the analysis may not be performed.

Statistical Analyses
Model Results Presentation

 Odds ratios, confidence intervals and p-values will be presented for all covariates specified in the model.
Sensitivity Analyses

 Not applicable
Subgroup Analyses

 Not applicable

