2.2. Study Objective(s) and Estimand(s) / Endpoint(s)

Objectives	Estimands/Endpoints
Primary	
To demonstrate the non-inferior antiviral activity of CAB LA + RPV LA every two months compared to a BIK single tablet regimen administered once daily over 12 months in suppressed HIV-1 infected antiretroviral therapy (ART)-experienced participants	Proportion of participants with plasma HIV-RNA greater than or equal to 50 copies/mL as per Food and Drug Administration (FDA) Snapshot algorithm at Month 12 (OLI and BIK)/Month 11 (D2I) (Intent-to-Treat Exposed [ITT-E] population)
Secondary	
To demonstrate the antiviral and immunologic response with the use of CAB LA + RPV LA every 2 months compared to a BIK single tablet regimen administered once daily	
Proportion of participants with plasma HIV-1 RNA <50 c/mL (c/mL) at Month 6 and Month 12 (OLI and BIK)/Month 5 and Month 11 (D2I) using the FDA Snapshot algorithm (Intent-to-Treat Exposed [ITT-E] population)
 
Proportion of participants with protocol-defined confirmed virologic failure (CVF) through Month 6 and Month 12 (OLI and BIK)/Month 5 and Month 11 (D2I).
 
Proportion of participants with HIV-RNA greater than or equal to 50 c/mL as per FDA Snapshot algorithm at Month 6, and Month 12 (OLI and BIK)/Month 5 and Month 11 (D2I)
 
Absolute values and changes from Baseline in viral load and CD4+ cell count over time including Month 6 and Month 12 (OLI and BIK)/Month 5 and Month 11 (D2I)

To assess viral resistance in participants experiencing protocol-defined confirmed virologic failure	Incidence of treatment emergent genotypic and phenotypic resistance to CAB, RPV, BIC, FTC, and TAF through Month 6 and Month 12 (OLI and BIK)/Month 5 and Month 11 (D2I).
To evaluate renal (in urine and blood) and bone (in blood) biomarkers in participants treated with CAB LA + RPV LA compared to BIK	Change from Baseline (Day 1) in renal and bone biomarkers at Months 6 and 12 (OLI and BIK)/Month 5 and Month 11 (D2I).
To evaluate Metabolic Syndrome for participants treated with CAB + RPV and BIK	Change from Baseline in proportions of participants with Metabolic syndrome at Months 6 and 12 (OLI and BIK)/Month 5 and Month 11 (D2I)

Objectives	Estimands/Endpoints
To evaluate insulin resistance in participants treated with CAB LA + RPV LA compared to BIK	Change from Baseline (Day 1) in homeostasis model of assessment-insulin resistance (HOMA-IR) at Months 6 and 12 (OLI and BIK)/Month 5 and Month 11 (D2I).

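### The metabolic-syndrome logistic model in SAP 8.5.2 leaves out baseline metabolic syndrome, which its other covariates replace only in part

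*SAP*

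**What the plan says.** SAP 2.2 gives the secondary endpoint as "Change from Baseline in proportions of participants with Metabolic syndrome at Months 6 and 12" (Months 5 and 11 for D2I). Section 8.5.2 defines the syndrome by component count: "Three abnormal findings out of the five risk factors would qualify a person for the metabolic syndrome". The five are waist circumference, triglycerides, HDL, blood pressure and fasting glucose, with cut-offs in 16.6.4.

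The planned model is stated as "A logistic regression model will be performed on the proportion of subjects with metabolic syndrome at Month 6", with a second fit at Month 12/11. Besides treatment, it has ten covariates: baseline CD4+ count, gender at birth, BMI class, age group, race, smoking, hypertension, and three metabolic terms, "Baseline Triglyceride (High vs. Normal", "Baseline HDL (Low, High vs Normal" and "Baseline HOMA-IR (2 to <3, 3 to <4, ≥4 vs <2". On hypertension it says: "Hypertension is defined as having a medical history of hypertension or use of medication treating hypertension (current and past". Baseline metabolic syndrome is not listed. No sensitivity analysis is planned for this model.

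**The concern.** The outcome is a yes/no status that can be determined on Day 1, and participants who start with it can be expected to be much more likely to have it later. Leaving out an outcome's own baseline usually costs efficiency. Here it also means that no planned treatment comparison conditions on baseline status, although 2.2 words the endpoint as a change.

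The SAP does otherwise elsewhere. Bone markers (8.4.1), renal markers (8.4.2), HOMA-IR (8.5.4) and HIVTSQs (13.5.1.1) all carry their own baseline. The closest comparator is the logistic sensitivity analysis of HOMA-IR thresholds in 8.5.4. It is also binary and metabolic, and it keeps the baseline value. The SAP gives no reason for treating metabolic syndrome differently.

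**Working it through.** **No figure to reproduce.** Section 8.5.2 states no power, alpha or sample size. The check compares the covariates with the outcome definition and then illustrates the size by simulation.

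**Is baseline status available?** Yes. The Appendix 2 schedules collect waist, vital signs, fasting glucose and fasting lipids on Day 1 for OLI, D2I and BIK. Table 3.65 (16.15.7) tabulates the shift from baseline as yes, no or missing.

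**Do the listed covariates stand in for it?**

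| Component (16.6.4) | Covariate in 8.5.2 | Coverage |
|---|---|---|
| Waist ≥102 cm (men), ≥88 cm (women) | BMI <30 or ≥30 kg/m² | proxy |
| Triglycerides ≥150 mg/dL | High or Normal | direct, cut not stated in 8.5.2 |
| HDL <40 mg/dL (men), <50 mg/dL (women) | Low, High or Normal | direct, cut not stated in 8.5.2 |
| Systolic ≥130 and/or diastolic ≥85 mm Hg | history or medication | proxy |
| Fasting glucose ≥100 mg/dL | HOMA-IR class (insulin × glucose / 22.5) | proxy |

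Two components enter directly and three by proxy. If the lipid classes are the NCEP ones in 16.6.4 (8.5.2 does not say), Low HDL is <40 mg/dL for everyone. A woman at 40 to 49 would then be abnormal for the syndrome but Normal in the model. Triglycerides of 150 to <200 mg/dL are Borderline High in NCEP, a class that 8.5.2 does not place.

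An example shows the gap. Take two women alike on every covariate: BMI 27, no hypertension history or medication, HOMA-IR below 2, triglycerides 210, HDL 38. Both have normal waist and glucose. One measures 135/80 on Day 1 and has 3 of 5 components; the other measures 120/75 and has 2 of 5. Only the first has baseline metabolic syndrome, and the model cannot tell them apart.

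**Size, by simulation.** Only N = 654 and the 2:1 allocation (436 vs 218) come from the SAP (2.3). The rest is assumed: component prevalences of 30 to 45%, between-component correlation 0.2, baseline syndrome about 30%, and follow-up about 30% (BIK) vs 38% (Q2M). Within-subject correlations were varied from 0.5–0.9 (low tracking) to 0.75–0.95 (high tracking). The fitted terms were treatment, BMI, triglycerides, HDL, hypertension history and HOMA-IR, with and without baseline status. There were 1,500 replicates per row.

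| Tracking | OR of baseline status given the other terms | Treatment log-OR (SE) without | with | Power without | with |
|---|---|---|---|---|---|
| low | 2.65 | 0.397 (0.197) | 0.410 (0.201) | 51.9% | 52.3% |
| middle | 3.49 | 0.419 (0.203) | 0.443 (0.210) | 54.1% | 55.7% |
| high | 5.80 | 0.459 (0.214) | 0.514 (0.227) | 58.1% | 62.9% |

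The differences in power are 0.4, 1.6 and 4.8 points. As is usual in logistic regression, adding a prognostic term raises the standard error slightly and moves the log-odds ratio further from zero. The gain is in their ratio: 0.459/0.214 = 2.14 against 0.514/0.227 = 2.26 in the last row.

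Under no treatment effect (600 replicates per row), type I error was 3.3 to 4.8% across both models. The Monte Carlo standard error at 5% is √(0.05 × 0.95 / 600) = 0.9 points.

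A second simulation assumed 15% baseline prevalence, N = 590 and baseline/post correlation of about 0.5. Power went from 64% to 68%, inside the same range.

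**The case against.** The strongest reply is that baseline is already largely covered. All five components are represented, and HOMA-IR contains fasting glucose by formula. The remaining gain is small, and this is a secondary safety model with no stated power or success criterion. The objective in 2.2 is to evaluate the syndrome in both groups; unlike its neighbours, it is not worded as a comparison with BIK. All of this stands, and it limits the weight of the point. It does not remove it, because baseline status kept an odds ratio of about 2.7 to 5.8 after SAP-type covariates.

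The reply also has force on model size. With treatment, the model has 1 (treatment) + 1 (CD4) + 1 (gender) + 1 (BMI) + 2 (age) + 2 (race) + 2 (smoking) + 1 (hypertension) + 1 (triglycerides) + 2 (HDL) + 3 (HOMA-IR) = 17 parameters. At an assumed 15% of 590 there are about 89 events, or 5 per parameter. Under the first simulation's inputs there are 0.304 × 218 + 0.377 × 436 ≈ 231 events, or about 14 per parameter. Section 8.5.2 allows the analysis to be dropped for separation, so a partly collinear extra term is not free.

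Three stronger readings are tempting but not supported:

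- **The odds ratio fails to address the change endpoint.** Randomisation makes expected baseline prevalence equal between arms, so the difference in follow-up proportions has the same expectation as the difference in changes. Table 3.65 also reports the shift descriptively.
- **Any chance imbalance in baseline prevalence passes straight into the odds ratio.** Randomisation is stratified by BMI and gender, and the component terms absorb part of the rest. Only the residual matters.
- **Baseline CD4 is a weak term that could make room.** Nothing in the SAP ranks the covariates.

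**Conclusion.** The omission is real and departs from the SAP's own practice. The treatment test is not biased. The model forgoes about 0 to 5 power points under the inputs tried, and it does not condition on baseline status while 2.2 words the endpoint as a change. The size rests on assumed prevalences, correlations and treatment effect and should be read as a range. The omission itself rests only on the text of 2.2, 8.5.2 and 16.15.7. This is a worthwhile, inexpensive improvement to a secondary safety analysis; it has no bearing on the primary conclusion.

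**What to change.** 1. Add baseline metabolic syndrome (yes/no) to the 8.5.2 covariates, or alternatively the baseline count of abnormal components (0 to 5).
2. State whether the new term supplements or replaces the overlapping baseline triglyceride and HDL terms, so that the parameter count and the risk of separation stay manageable. As a supplement it adds one parameter, giving 18. Replacing the triglyceride term (1) and the HDL terms (2) gives 17 − 3 + 1 = 15.
3. Align the endpoint wording in 2.2 and 8.5.2, for example as status at the visit adjusted for baseline status.

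No new data are needed, and Table 3.65 already requires the derivation. The cost is a short text change and, if the term is a supplement, one partly collinear parameter.

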8.5.4. HOMA-Insulin Resistance

HOMA-Insulin Resistance analysis will only be performed when all expected data through Month 12 (OLI and BIK)/Month 11 (D2I) has been received from the laboratory. Statistical estimates for each planned visit will be provided in the Month 12 primary analysis using the MMRM model as describe in the below sections unless otherwise noted. The details of the planned displays are in [Appendix 15: List of Data Displays](#).

Statistical Analyses
Endpoints

 Change from baseline in HOMA-IR at Month 6 (OLI and BIK)/Month 5 (D2I) and at Month 12 (OLI and BIK)/Month 11 (D2I) 
Note: the following subjects will be excluded from the statistical analysis:
 
 diabetic or have taken an anti-diabetic medication up to screening fasting glucose >126mg/dl and HbA1C >6.5% at Day 1 have had a cosmetic procedure including liposuction/liposculpture of the thighs, buttocks, hips and/or abdomen
Covariates

Statistical Analyses

 • Baseline Value (continuous) • Gender at Birth (male, female) • Baseline BMI(<30 kg/m², >=30 kg/m²) • Age (Continuous) • Race (White, Black/African American, Other) • Smoking Status (Never, Current, Former) • Hypertension (Yes vs no) 
Note: Hypertension is defined as having a medical history of hypertension or use of medication treating hypertension (current and past)

Data Handling

 • OC (Observed Case) dataset will be used.
Model Specification

 • Same as in Section 8.4.1
Model Checking & Diagnostics

 • Same as in Section 8.4.1
Model Results Presentation

 • Same as in Section 8.4.1
Sensitivity Analyses

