
 • Logistic regression models will be performed on the proportion of subjects with HOMA-IR >=2, >=3 or >=4 at Month 12(OLI and BIK)/11(D2I) adjusting for the same covariates as specified in the MMRM analysis (without visit or interaction terms and without log transformation for the baseline value). Odds ratios, confidence intervals and p-values will be presented for all covariates specified in the model. • Upon delivery of data, an assessment regarding the amount of missing data will be made. If the amount of missing HOMA-IR outcome data considered as a result of other impacts such as COVID-19 is substantial, the logistic regression analysis may not be performed. • If the percent of subjects above any of the cutoffs are below 5% of the total number of subjects (observed data), or if complete or quasi-complete separation is observed in the data, then the analysis may not be performed.
Subgroup Analyses

 • Not applicable

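### Section 8.5.2 lets the adjusted metabolic-syndrome comparison be skipped for separation on a sparse covariate level, although the treatment odds ratio can still be estimated

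*SAP*

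**What the plan says.** Section 2.2 lists a secondary objective: "To evaluate Metabolic Syndrome for participants treated with CAB + RPV and BIK". Its endpoint is the change from baseline in the proportion with the syndrome at Months 6 and 12 (OLI and BIK) or 5 and 11 (D2I).

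Section 8.5.2 gives the analysis: "A logistic regression model will be performed on the proportion of subjects with metabolic syndrome", adjusted for ten covariates, several of them with three or four levels, such as "Baseline HOMA-IR (2 to <3, 3 to <4, ≥4 vs <2". Sensitivity and subgroup analyses are marked as not applicable.

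Under model checking, the section gives grounds for leaving the model out. One is a prevalence floor: "If the percent of subjects are below 5% of the total number of subjects (observed data". Another is separation: "if complete or quasi-complete separation is observed in the data, then the analysis may not be performed". No alternative method is named for either.

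Section 8.5.4 repeats the separation clause for the HOMA-IR logistic models ("or if complete or quasi-complete separation is observed in the data, then the analysis may not be performed"), but those models stand under sensitivity analyses. The main HOMA-IR analysis is described this way: "Statistical estimates for each planned visit will be provided in the Month 12 primary analysis using the MMRM model".

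**The concern.** Quasi-complete separation occurs as soon as one level of a categorical covariate has no events or only events. That is a problem for the coefficient of that level. It does not remove the information on treatment. The clause in 8.5.2 does not make this distinction, so a small nuisance category can be the reason for not reporting the treatment comparison.

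Sparse levels are foreseeable here. Baseline triglycerides, HDL and hypertension are covariates, and they overlap with components of the outcome defined in section 16.6.4. If the HDL levels are the NCEP categories of 16.6.4, which the labels match, the high level starts at 60 mg/dL. The syndrome counts HDL as abnormal only below 40 (men) or 50 (women), so few events are expected in that level.

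At stake is the adjusted odds ratio in Table 3.66, due at both Month 6 and Month 12. Because the clause is permissive, the decision is taken at each delivery after the data are in, and the two decisions could differ.

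**Working it through.** The SAP gives no event count, prevalence or power for this model, so there is no plan figure to reproduce.

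**Size of the model (8.5.2).** CD4 1, gender 1, BMI 1, age 2, race 2, smoking 2, hypertension 1, triglycerides 1, HDL 2, HOMA-IR 3: 16 degrees of freedom. Treatment, which the covariate list omits but an adjusted comparison presupposes, makes 17.

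**Events at the plan's floor.** With about 654 participants (section 2.3), all observed, 0.05 × 654 = 32.7, about 33 events, and 33 / 17 = 1.9 events per parameter. At 10% prevalence it is 65 / 17 = 3.8 and at 20% 131 / 17 = 7.7.

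**One sparse level.** If a level holds m participants with event probability p, the chance of no events or only events is (1 − p)^m + p^m. For p assumed at 10%, 20% and 30%:

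- m = 10: 35%, 11%, 2.8%
- m = 20: 12%, 1.2%, 0.1%
- m = 30: 4.2%, 0.1%, about 0

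**The whole covariate set.** Two sets of simulated trials counted how often at least one categorical level had no events or only events. Set A used 1,500 trials per setting, two effect strengths and 450 or 560 observed participants. Its assumed shares were BMI ≥30 20%, hypertension 20%, high triglycerides 25%, HDL low and high 20% each, HOMA-IR levels 50/20/12/18% and race Other 10%. Set B kept these shares and assumed different effects and different remaining shares.

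| Prevalence | A, n = 450 | A, n = 560 | B |
|---|---|---|---|
| 5% | 48-67% | 34-57% | 13-34% |
| 8% | 20-40% | 11-30% | 2-11% |
| 10% | 9-27% | 6-19% | 0.5-5% |
| 15% | 1.5-9% | 0.6-5% | under 1% |
| 25% | 0-0.4% | 0-0.1% | none |

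**What separation does to the treatment estimate.** When a level has no events, its coefficient tends to minus infinity and its participants' likelihood contribution tends to 1. The other estimates then equal those from a fit without these participants. A single data set illustrates this: 654 participants at 2:1 (436 and 218), a BMI covariate, no true treatment effect, 155 events, and one 12-participant level set to no events.

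- Maximum likelihood: treatment odds ratio 0.798 (95% CI 0.540-1.179), the same at 15 and 20 iterations. The separated level's coefficient moved from −14.9 to −19.9.
- Firth: 0.797 (Wald 95% CI 0.540-1.177), with a finite coefficient of −2.01 for the level.
- Excluding the level's participants: 0.798 (0.540-1.179).
- Dropping that covariate: 0.811 (0.550-1.197).

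This data set has four parameters including the intercept and a prevalence of 155 / 654 = 24%. It shows the mechanism and says nothing about how well a 17-parameter model behaves at 1.9 events per parameter.

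**Separation by treatment itself.** With 218 BIK participants and 5% prevalence, the chance of no BIK event is 0.95^218, about 0.00001. The clause would in practice be triggered by covariates.

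**The case against.** The case for leaving the text alone has real weight.

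- **The endpoint survives.** The objective says evaluate and, unlike the HOMA-IR objective ("To evaluate insulin resistance in participants treated with CAB LA + RPV LA compared to BIK"), does not say compared to BIK. Tables 3.64 and 3.65 report percentages and shifts by arm with no separation condition. This stands: a reader might infer that the secondary endpoint is lost, and the SAP does not support that.
- **HOMA-IR is not exposed.** A reader might extend the point to the HOMA-IR objective because 8.5.4 has the same clause. There the logistic models are sensitivity analyses, and the MMRM, which gives the treatment comparison, has no separation clause.
- **The rule is permissive, and categories can be merged.** Section 5.4.2 allows small subgroup categories to be combined before unblinding. Its list includes BMI, gender, age and race but not triglycerides, HDL or HOMA-IR, so it covers only part of the model.
- **The syndrome may not be rare.** The note to Safety Figures 3.11-3.13 restricts the Month 12 profile plots for lack of space, which suggests a fair number of cases. That is suggestive only, but it points to the rows of the table where the risk is small.
- **Firth does not cure an overloaded model.** At about 33 events for 17 parameters, finite estimates are still fragile. This also stands. Other remedies gave nearly the same treatment estimate in the example, so Firth is one sound choice among several.
- **No sign of selective reporting.** A reader might suspect this in an open-label trial. Separation is an objective condition, and nothing in the SAP shows that using the clause would favour an arm.

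**Conclusion.** The point holds for section 8.5.2. The clause allows the only model-based between-arm analysis of metabolic syndrome to be left out because of a nuisance covariate level, when the treatment odds ratio remains estimable. The loss is limited to the adjusted odds ratio.

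Taking both simulation sets together, the chance is roughly 13-67% at 5% prevalence, 0.5-27% at 10%, at most 9% at 15% and about nil at 25%. These ranges rest on assumed level shares, effects and observed numbers, none of which the SAP states. The upper end at 5% applies only at the plan's own floor and should not be read as the expected risk. The SAP supports neither the stronger claim that a secondary comparison is lost for HOMA-IR nor the claim that the metabolic-syndrome endpoint goes unreported. The point is minor, and worth making because the remedy costs almost nothing.

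**What to change.** In section 8.5.2, replace the separation clause with: *if complete or quasi-complete separation is observed, the same model will be fitted with Firth's penalised likelihood and profile-likelihood confidence intervals, reported with a footnote.* The 5% prevalence clause can stay as it is.

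The same sentence may be used in section 8.5.4 for consistency. It does not change what supports the HOMA-IR objective.

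The cost is one sentence and one program option (FIRTH). Nothing changes if separation does not occur. If it does, estimates are shrunk slightly, and the low number of events per parameter near the 5% floor remains a limitation to state beside the result.
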